To address this hypothesis, in the present study we propose to conduct a prospective, randomised controlled study in patients with protective stoma, aiming to investigate whether stimulation of stoma drainage fluid through the anus to an open intestinal segment prior to stoma closure is beneficial for the recovery of bowel function, reduction of complications and improvement of intestinal dysbiosis, and to provide high-level evidence for the clinic.

II. Purpose of the study

To analyse the occurrence of defecation complications, rectal function and quality of life indicators after collecting stoma discharge for anal re-infusion to patients after performing protective ileostomy in anus-preserving surgery for middle and low rectal cancer, so as to evaluate the impact of collecting stoma drainage fluid for anal re-infusion on the recovery of patients' intestinal function.

III. Subject of the study

(i) Inclusion criteria

1. Age: 18~75 years old, male or female;
2. Pathological diagnosis of adenocarcinoma of the rectum on preoperative biopsy;
3. Clinical staging was T1-4aN0-2M0;
4. No distant multiple metastases;
5. ECOG rating 0-2;
6. Cardiac, pulmonary, hepatic and renal functions met the criteria for surgical tolerance
7. Clinical diagnosis of middle and low rectal cancer, the lower edge of the tumour is within 10cm from the anal verge, and it is proposed to perform radical rectal surgery and prophylactic ileostomy at stage I, and intestinal closure at stage II;
8. Patients and their families were able to understand and willing to participate in this clinical study and signed an informed consent form.

(ii) Exclusion criteria

1. Previous history of malignant colorectal tumour or recently diagnosed combination of other malignant tumours;
2. Patients with combined intestinal obstruction, intestinal perforation, intestinal haemorrhage, etc. requiring emergency surgery;
3. Neighbouring organs requiring combined organ removal;
4. ASA classification \geq Grade IV and/or ECOG physical status score > 2 ;
5. Those who have serious liver and kidney dysfunction, cardiopulmonary dysfunction, coagulation dysfunction or combined serious basic diseases cannot tolerate the surgery;
6. Have a history of serious mental illness;
7. Pregnant or breastfeeding women;
8. Those who have a history of taking steroid drugs;

9. Patients with other clinical and laboratory conditions considered by the investigator to be inappropriate for participation in the trial;

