10. One week before the operation, there are signs of infection, body temperature rises $>37.5^{\circ}\text{C}$, blood WBC $>10.0 \times 10^9/\text{L}$;
11. History of antibiotic use 1 week prior to surgery (excluding preoperative shock medication);
12. Preoperative neoadjuvant patients

(iii) Exit criteria

1. Accompanied by other non-oncological conditions that make it impossible for the patient to continue to receive this treatment plan;
2. After enrolment in the study, patients who required emergency surgery due to intestinal obstruction, perforation, or bleeding, et al. prior to stoma closure;
3. Patients with pathologically confirmed distant metastases after rectal surgery, including liver, pelvis, ovary, peritoneum, and distant lymph node metastases;
4. Intraoperative exploration for middle and low rectal cancer in anus-preserving surgery for those who need combined organ resection;
5. After enrolment in the study, patients requested to withdraw from the study cohort for various reasons, or were unable to complete the study programme and follow-up for various reasons;
6. Anastomotic fistula, severe anastomotic stenosis (inability to pass through enteroscopy or oesophageal finger and inability to dilate via oesophageal finger) after radical rectal surgery.

IV. Study endpoints

(i) Primary study endpoints:

Incidence of major LARS after 6 months of stoma closure.

(ii) Secondary research endpoints:

1. Bacteriological sequencing 1 month after stoma closure

[figure not shown]
2. Anorectal function (LARS questionnaire, Wexner¹⁵ incontinence score, MSKCC¹³⁻¹⁴ bowel function questionnaire), Glazer pelvic floor muscle surface electromyography, and quality of life scores after 1 month of stoma return.

3. Recovery of postoperative bowel function

After reversal surgery, time to oral feeding, time to anal defecation after reduction surgery, and rate of intestinal obstruction (intestinal obstruction was defined as ,inability to tolerate food for more than 72 H or the need for re-fasting or gastrointestinal decompression) were observed.

V. Research design

The study was a prospective randomised design with simple randomised grouping, randomised by prior computer-generated random number tables. The expected recruitment cut-off date for all subjects was 1 November 2022, with a predictable sample size of 60 cases to be enrolled based on patient admissions to the hospital. The enrolment process is as follows

(i) Transanal reinfusion of stoma discharge

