sampling node

Before radical rectal surgery, before stoma closure surgery, and 1 month after stoma closure surgery.

(v) Hospitalisation and discharge criteria after stoma closure surgery

1. Hospitalisation

Discontinue all IV medications on postoperative day 2 if they meet the following criteria:.

- Haemodynamically stable
- Temperature < 37.3 degrees Celsius
- Pain score < 5 (on a scale of 0 to 10)
- Tolerates oral diet without nausea or vomiting
- Clear urination

If all criteria are not met the morning after surgery, the patient will continue rehydration, anti-infective, and pain control therapy until the criteria are met. In addition, even if all criteria for stopping intravenous medication are met, treatment may continue to be given if the surgeon feels that it would be beneficial for the patient to have continued treatment. Patients are checked in daily to see how they are doing to ensure they are progressing well.

2. Discharge criteria

The patient is in good general condition, basically resuming normal diet and intestinal function; body temperature is normal and there are no positive signs on

abdominal examination; relevant laboratory findings are basically normal; and the abdominal incision is healing well (II/A or II/B).

(vi) Adverse events

1. The patient is unable to operate the transanal reinfusion process

Treatment: Each patient who needs transanal reinfusion will have the first process performed by the doctor, who will instruct the patient and his/her family on the spot. The doctor and the patient leave each other's phone number or WeChat to keep in touch.

2、Abnormalities in the patient's transanal reinfusion

Handling: If the patient has abdominal distension or the urge to defecate during transanal reinfusion, the patient should be instructed to take deep breaths to alleviate the discomfort. During transanal reinfusion, pay attention to the patient's condition changes at any time, such as the discovery of rapid pulse, pallor, cold sweat, severe abdominal pain, panic and shortness of breath, you should immediately stop the enema and contact the doctor in time to take emergency measures.

VI. Follow-up programme

Functional learning follow up:

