1. General principles: All statistical tests will be two-sided, and $P < 0.05$ will be considered statistically significant for the differences tested. The description of quantitative indicators will calculate the mean, standard deviation, median, minimum value, maximum value, if it meets the normal variance chi-square, expressed as the mean \pm standard deviation, and use the t-test to compare the differences between the two groups; data that do not meet the normal variance chi-square are expressed as the median (quartile), and the rank sum test is used for comparison. Categorical indicators were described by the number of cases and percentages in each category, and the chi-square test was used to compare the differences between the experimental and control groups.

2. The main outcome indicators of the occurrence of LARS at 6 months after the

reduction were expressed as the number of cases (percentage), and the chi-square test was used to compare the differences between the experimental group and the control group.

Secondary outcome indicator colony species results will be tabulated based on the top 15 species in abundance using cumulative histograms to compare species composition differences between samples. Based on the species abundance information of each sample at the genus level, the top 50 genera of abundance will be selected, and the samples and species will be clustered based on the abundance information of each sample, and heat maps will be drawn. And Shannon diversity index, Simpson index and Chao1 richness index were calculated for Alpha diversity analysis Comparative analysis of microbial community composition of samples between different groups was performed using Beta diversity analysis.

Secondary outcome indicators Wexner score, MSKCC Bowel Function Questionnaire, and QLQ-C30 Quality of Life Scale scores were analysed for repeated-measures data between the two groups, Mauchly's test of sphericity was performed, and ordinary one-way ANOVA or multifactorial ANOVA was performed according to the test results.

x. schedule of visits

| | | | | | | |
|---------------------------------------|--------------------------------------|-------------------|-------------------------------------|--------------------------------------|---------------------------------------|---------------------------------------|

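### The pre-surgery flora sample is collected from every patient but has no role in the flora analysis, which costs precision and leaves the beta-diversity comparison without a direction

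*Combined protocol and SAP*

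**What the plan says.** - **Aim.** The last paragraph of the introduction lists three benefits to be investigated. Besides recovery of bowel function it names "reduction of complications and improvement of intestinal dysbiosis". Section II, the formal purpose, begins "To analyse the occurrence of defecation complications, rectal function and quality of life indicators" and does not mention flora.
- **Endpoint.** The first secondary endpoint in Section IV (ii) is "Bacteriological sequencing 1 month after stoma closure". It has no metric and no direction, and dysbiosis is not defined anywhere.
- **Samples.** Section V (iv), sampling node, gives "Before radical rectal surgery, before stoma closure surgery, and 1 month after stoma closure surgery". Section VII item 2 and the schedule of visits agree.
- **Flora analysis, Section X (ii) 2.** The 15 most abundant species are tabulated "using cumulative histograms to compare species composition differences between samples", and the top 50 genera go into a clustered heat map. For diversity, "Shannon diversity index, Simpson index and Chao1 richness index were calculated for Alpha diversity analysis", and then "Comparative analysis of microbial community composition of samples between different groups was performed using Beta diversity analysis". The groups are not defined, and no distance measure, test or time point is named.
- **Default tests, Section X (ii) 1.** Quantitative indicators are compared between the two arms by an unpaired t-test or a rank-sum test.
- **Repeated measures.** The next paragraph of Section X (ii) 2 plans a repeated-measures analysis for the Wexner, MSKCC and QLQ-C30 scores only.

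**The concern.** The plan pays for a pre-surgery sample from every patient and then gives it no part in the analysis. Flora differs widely from person to person. Part of that variation would be explained by the patient's own earlier sample; in the planned comparison it all stays in the error term. Allocation is by simple randomisation of 60 patients, so some chance imbalance at baseline is also likely.

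The second problem is interpretation. A beta-diversity comparison can show that two sets of communities differ, but it gives no order between them. Reinfusion puts stoma discharge into the distal bowel, so the arms could differ merely because organisms were carried over. Without a reference point, such a difference could not support a statement that dysbiosis improved. The introduction attributes dysbiosis to surgery and diversion, so on the protocol's own reasoning the pre-surgery sample is the obvious reference.

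**Working it through.** **1. Is the pre-surgery sample used?** Each item in Section X (ii) 2 was compared with the sampling times in Section V (iv).

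| Planned item | Link to the patient's pre-surgery sample |
|---|---|
| Top-15 species histograms | none stated |
| Top-50 genera clustering and heat map | none stated |
| Shannon, Simpson, Chao1 | none stated; the unpaired default test applies |
| Beta diversity | none stated; groups undefined |

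The protocol plans for repeated measurements elsewhere (the questionnaires), but not for flora.

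**2. Number per arm.** No sample size is given for flora, so the primary-endpoint figure in Section IX is used. Inputs: 14% and 47%, two-sided 0.05, 80% power. With unpooled variance:

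n = (1.960 + 0.842)² × (0.14×0.86 + 0.47×0.53) / 0.33² = 26.63, so 27.

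Allowing for 10% dropout, 27/0.9 = 30 per arm, or 60 in all. The protocol's 27 is therefore reproduced if read as per arm.

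**3. Is the unlinked 1-month comparison biased?** Section V says "The study was a prospective randomised design with simple randomised grouping". Under randomisation the expected baseline difference between arms is zero, so the 1-month difference estimates the effect of reinfusion. A simulation of 20,000 trials with 27 per arm and a true effect of 0.6 SD gave mean 1-month differences of 0.604, 0.599 and 0.598 at baseline correlations of 0.3, 0.5 and 0.7. With no effect the means were 0.002, −0.001 and −0.001. There is no bias.

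**4. What does the baseline add?** The assumptions are mine: one alpha index scaled to SD 1, correlation r between the pre-surgery and 1-month values of 0.3 to 0.7, 27 per arm, normal approximation.

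- 1-month value only: detectable difference = (1.960 + 0.842) × √(2/27) = 0.762 SD.
- Pre-surgery value as covariate: multiply by √(1 − r²); the variance falls by r².
- Plain change score: multiply by √(2(1 − r)).

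| r | Variance cut with covariate | Detectable, 1-month only | Detectable, covariate | Detectable, change score |
|---|---|---|---|---|
| 0.3 | 9% | 0.762 | 0.727 | 0.902 |
| 0.5 | 25% | 0.762 | 0.660 | 0.762 |
| 0.7 | 49% | 0.762 | 0.545 | 0.591 |

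For an assumed effect of 0.6 SD, power is 60% with the 1-month value only, and 64%, 72% or 87% with the covariate. The change score gives 46%, 60% or 81%. It is less precise than ignoring the baseline when r is below 0.5, so how the baseline enters the analysis matters.

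**The case against.** The strongest reply is that randomisation already does the work. The endpoint is fixed at 1 month, the arms are randomised, and an arm difference at that time is a valid estimate whether or not the pre-surgery sample is used. That stands in full. A reader might infer that, without within-patient linkage, the plan can show that the arms differ but cannot show whether reinfusion improved the flora. The documents do not support that. The three alpha indices are ordered quantities with a default test, the species and genus displays show which organisms differ, and the background names Bifidobacterium and Lactobacillus as beneficial. None of this is a pre-specified measure of dysbiosis, but the plan has more than a directionless comparison.

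It can also be said that pairing would not define improvement, because the pre-surgery flora comes from a tumour-bearing bowel. This stands too. It limits what a distance from baseline may be said to show, and it is why that distance is proposed only as a supportive analysis.

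A reader might further infer that the three samples per patient will be pooled as if independent, which would inflate the false-positive rate. Section X (ii) 2 leaves the groups undefined, so the wording does not exclude this. But the plan does not state it, and Section IV points to the 1-month sample alone. No inflated error rate can be attributed to the plan.

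**Conclusion.** The point holds as a matter of precision and interpretability, not of bias. The pre-surgery sample has no stated use, and the beta-diversity comparison has no direction with which to support an improvement in dysbiosis.

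The gain from adjustment depends on a correlation that the documents do not give: slight at 0.3 (9% less variance) and substantial at 0.7 (49%). The detectable differences also assume 27 evaluable patients per arm. Absence of bias presumes that 1-month samples are not missing selectively by arm, which linkage to baseline would not cure.

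Severity is minor to moderate. Flora is a secondary endpoint and one of several aims in the introduction; it is absent from Section II, and the sample size does not rest on it.

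**What to change.** In Section X (ii) 2:

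1. **Alpha diversity.** Compare Shannon, Simpson and Chao1 at 1 month between arms, with the patient's own pre-surgery index as covariate. Do not use plain change scores. Take the covariate from the sample before radical surgery; the pre-closure sample comes after reinfusion has begun and is not a baseline. State how a missing pre-surgery index is handled.
2. **Beta diversity.** Name one distance metric and one test, and restrict the arm comparison to the 1-month samples. If several sampling times are used, permute whole patients rather than single samples.
3. **Supportive analysis.** For each patient, compute the distance on that metric between the 1-month and the pre-surgery sample, and compare it between arms by the rank-sum test. Report it only as *return to pre-surgery flora*, not as improvement of dysbiosis.
4. **Direction.** State in advance which result would count as improvement, or make no such claim. Histograms and heat maps stay descriptive.

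The cost is SAP wording and a little analysis, with no new samples. The drawback is that patients without a usable pre-surgery sample drop out of the distance measure.

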Experimental group:

Starting from 1 month after radical rectal surgery, the infusion is performed once a week for 2 months. Each infusion was performed with a liquid diet on the day before, and 400-600 mL of stoma discharge was collected on the same day (if the stoma fluid was limited, it could be blended with warm water), and the reinfusion was performed from the patient's anus using an enema bag, with a flow rate of about 100 mL/min being controlled.

Control group:

No special treatment.

(ii) Preoperative preparation for protective stoma reduction

Stoma closure was performed 3 months after surgery. All patients were reviewed in an outpatient clinic at least 7 days before preparation for stoma closure.

The surgeon is responsible for performing rectal palpation and Lower gastrointestinal tract imaging to rule out anastomotic leakage and anastomotic stenosis.

(iii) Pelvic floor muscle function assessment

Pelvic floor muscle function tests were performed "prior to radical rectal surgery", "prior to stoma closure surgery", "1 month after stoma closure surgery", "3 months after stoma closure surgery" and "6 months after stoma closure surgery" to compare the recovery of pelvic floor muscle function.

(iv) Sequencing of intestinal flora

faecal sampling

Gut microbiological samples were collected using the rectal swab method. Firstly, the perianal area was cleaned using soap, water and 70% alcohol respectively, then a sterile swab was inserted into the anus 4-5cm at the anal sphincter after moistening with saline and gently rotated to take a sample at the anal crypt (traces of faeces were clearly visible on the swab), then inserted into a sterile freezing tube (or the head of the swabs was clipped and dropped into a sterile freezing tube, 3-5 swabs were provided for each sample) and placed in a box containing ice/ dry ice in a foam box,

transported to the laboratory within 24h and stored in a -80°C refrigerator.

Sample delivery

- A. DNA: total amount >500ng, concentration >20ng/ul, no significant degradation, 2g of faecal or intestinal contents;
- B. The sample volume of a single delivery should be ≥ 20 samples, the delivery tube (freezing tube) must be clearly labelled with the sample number, the mouth of the tube should be sealed with Parafilm sealing film (to prevent cross contamination between samples), and the completed delivery order should be sealed in a self-sealing bag and sent to the laboratory with the samples transported on dry ice.

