(1) Items: including LARS score, Wexner incontinence score, MSKCC bowel function questionnaire; quality of survival score. The questionnaire follow-up was conducted by a professional pelvic floor follow-up team. The investigators of the pelvic floor follow-up team had appropriate professional training and were unaware of the patient grouping. The method of answering the questionnaires was explained to the patients before the questionnaire assessment, and after detailed enquiry, the patients were asked to answer the questionnaires in a specific way.

(2) Time: before radical rectal surgery, 1 month after stoma closure, 3 months after stoma closure and 6 months after stoma closure.

Survival follow-up:

Patient survival at 1 year post-stoma closure, 2 years post-stoma closure, 3 years post-stoma closure, and 5 years post-stoma closure follow up.

VII. Observation indicators

1. Baseline information: gender, age, height, weight, ASA, past medical and treatment history, co-morbidities, laboratory tests and imaging.
2. Sequencing of intestinal flora: before radical rectal surgery, before stoma closure, and 1 month after stoma closure.
3. Perioperative period: also include time to first postoperative defecation, time to first postoperative semi-liquid diet, and incidence of postoperative intestinal obstruction.
4. Follow-up indicators: LARS syndrome score, Wexner score, MSKCC Bowel Function Questionnaire, QLQ-C30 Quality of Life Scale.

VIII. Signing of informed consent and registration of subjects

(i) Informed consent signing:

The study will be conducted in accordance with clinical trial protocols, GCP principles and the Declaration of Helsinki. The informed consent form will be signed by the PI or a qualified, trained and authorised clinical staff member. The trial process needs to be explained in detail to the subject and/or authorised person, and it is important to avoid over-informing and to give the subject and/or authorised person enough time to consider whether to participate or not. Subjects/authorised persons will be enrolled in the experimental group once they have agreed and signed the informed consent form. The original informed consent form is kept on file at the research centre and a copy is retained by the subject.

(ii) Subject registration

After signing the informed consent form, patients are registered with subject information, baseline data, and oncology-related data, which should include all data from the screening phase of this study.

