| sports event | Pre-radi cal rectal surgery | pre-discha rge | Pre-sto ma closure surgery | Post-sto ma closure 1 month | Post-sto ma closure 3 months | Post-sto ma closure 6 months |
| Demographic information | ✓ | | | | | |
| Baseline assessment | ✓ | | | | | |
| bacterial colony sequencing | ✓ | | ✓ | ✓ | | |
| Pelvic floor muscle examination | ✓ | | ✓ | ✓ | ✓ | ✓ |
| surgical treatment | | ✓ | | | | |
| postoperative pathology | | ✓ | | | | |
| postoperative follow-up | | | | ✓ | ✓ | ✓ |

| | | | | | | |
|--|---|--|---|---|---|---|
| rectal examination | | | ✓ | ✓ | ✓ | ✓ |
| Pelvic floor surface electromyography assessment | ✓ | | ✓ | ✓ | ✓ | ✓ |
| Functioning, quality of life questionnaire | ✓ | | | ✓ | ✓ | ✓ |

Schedule 1

LARS Bowel Function Questionnaire

Does the patient complain of abnormal bowel movements: Yes No
Patient complained of abnormal defecation as: increased frequency incontinence painful defecation inability to distinguish between gas and faeces other

Whether the patient is satisfied with the current state of defecation:
Satisfied Unsatisfied

Does the patient think that the current state of defecation affects daily life:

No effect Yes effect

Use of medication to improve bowel movements: Yes Name _____ No

Prophylactic fistula Yes No

Prophylactic Fistula Payback Time is time Year Month Day
No

1. Have you ever had uncontrollable flatulence (farting)?

| | |
|--------------------------------|---|
|  Never | 0 |
| points | |
| Yes, less than 1 time per week | 4 |
| points | |
| Yes, at least once a week | 7 |
| points | |

2. Have you ever had an accidental leakage of loose stool?

| | |
|--------------------------------|---|
|  Never | 0 |
| points | |
| Yes, less than 1 time per week | 3 |
| points | |
| Yes, at least once a week | 3 |
| points | |

3. How many times a day do you have a bowel movement?

| | |
|---|---|
|  More than 7 times per day (24 hours) | 4 |
| points | |
|  4~7 times per day (24 hours) | 2 |
| points | |
|  1~3 times per day (24 hours) | 0 |
| points | |
|  Less than 1 time per day (24 hours) | 5 |

points

4. Have you ever had to have another bowel movement within an hour of having one?

Never

0

points

Yes, less than 1 time per week

9 points

Yes, at least once a week

11

points

5. Have you ever had to flush to the loo because of an urgent bowel movement?

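### The repeated-measures ANOVA of Wexner, MSKCC and QLQ-C30 leaves unused, as a covariate, the pre-surgery score the trial already collects; adjusting for it would be a free gain in precision

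*Combined protocol and SAP*

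**What the plan says.** Section X (ii) 2 states that the Wexner, MSKCC and "QLQ-C30 Quality of Life Scale scores were analysed for repeated-measures data between the two groups". Mauchly's test of sphericity comes next, and then "ordinary one-way ANOVA or multifactorial ANOVA was performed according to the test results". The section does not say which visits form the outcome, whether the arm effect or the arm-by-visit interaction is the test, or whether the pre-surgery score is adjusted for. No other section adjusts these scores for baseline.

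Section VI sets the questionnaire times: "before radical rectal surgery, 1 month after stoma closure, 3 months after stoma closure and 6 months after stoma closure". The visit schedule agrees. Its row "Functioning, quality of life questionnaire" is ticked at those four visits and not before stoma closure.

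Section V (i) gives the timing of the intervention: "Starting from 1 month after radical rectal surgery, the infusion is performed once a week for 2 months". The first questionnaire therefore precedes any reinfusion, and it is the only pre-treatment score available.

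Section IV (ii) 2 places the secondary endpoint at a single time, with "quality of life scores after 1 month of stoma return".

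**The concern.** Reinfusion cannot have affected the pre-surgery score, so the expected arm difference at that visit is zero. Its natural use is as a covariate that removes between-patient variation from the post-closure comparison. The plan does not use it in that way, and what happens instead depends on choices left open:

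- All four visits as outcome levels, arm main effect reported: the effect is averaged over a visit where it must be zero.
- All four visits, arm-by-visit interaction tested: no dilution, but an effect in one direction is spread over 3 degrees of freedom.
- Post-closure visits only: valid and undiluted, but information already collected is not used.

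Rectal function and quality of life are part of the stated purpose in Section II, and the trial has 60 patients. The precision of these comparisons matters, even though they are secondary.

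**Working it through.** **The plan's own figure.** No power, SD, effect size or correlation is given for these three scores. The only sample size figure is for major LARS in Section IX (14% v 47%, 80% power, two-sided 0.05). The unpooled two-proportion formula gives (1.960 + 0.842)² × (0.14×0.86 + 0.47×0.53) / 0.33² = 26.6, so 27 per arm. Then 27/0.9 = 30 per arm, or 60 in total. The stated 27 therefore reproduces as a per-arm number, and I use it below.

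**Inputs.** From the documents: n = 27 per arm; one pre-treatment and three post-closure visits; two-sided 0.05 ("All statistical tests will be two-sided, and $P < 0.05$ will be considered statistically significant"). Assumed: a constant post-closure effect d = 0.6 SD, unit variance at every visit, and compound symmetry with correlation ρ.

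**Dilution.** With complete data, the arm effect over four visits is (0 + d1 + d2 + d3)/4. This is 3/4 of the mean post-closure effect, whatever the pattern of d1 to d3 and whatever ρ. With d = 0.6 the estimate is 0.45.

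**Variance of each patient's summary.**
- Four-visit mean: (1 + 3ρ)/4, with effect 0.75d.
- Three-visit post-closure mean: (1 + 2ρ)/3, with effect d.
- Post-closure mean adjusted for baseline: (1 + 2ρ)/3 − ρ², with effect d.

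Power comes from the noncentral t with noncentrality effect/√(2V/27). The degrees of freedom are 52, or 51 with the covariate. For arm-by-visit it comes from the noncentral F on 3 and 156 df, with noncentrality (27/2) × 0.75 × d²/(1 − ρ).

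**At ρ = 0.5.**
- Four visits: V = 0.625, 0.45/√(2×0.625/27) = 2.09, power 53.7%.
- Arm-by-visit: 13.5 × 0.75 × 0.36/0.5 = 7.29, power 59.7%.
- Post-closure, unadjusted: V = 0.667, 0.6/√(2×0.667/27) = 2.70, power 75.5%.
- Post-closure, adjusted: V = 0.417, 0.6/√(2×0.417/27) = 3.42, power 91.8%.

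A simulation of 20,000 trials at this setting gave 54.1%, 75.7% and 91.4% for the three t-based analyses. Each rejected about 5% of the time with no effect.

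**Across ρ (power, %).**

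| ρ | Four visits, arm effect | Arm-by-visit | Post-closure, unadjusted | Post-closure, adjusted | Gain, adjusted over unadjusted (points) |
|---|---|---|---|---|---|
| 0 | 90.1 | 32.1 | 96.3 | 96.3 | 0 |
| 0.2 | 72.8 | 39.5 | 88.6 | 91.2 | 3 |
| 0.3 | 65.3 | 44.7 | 84.2 | 90.1 | 6 |
| 0.5 | 53.7 | 59.7 | 75.5 | 91.8 | 16 |

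**Relaxing the single correlation.** Only the pre-post correlation q drives the covariate gain. Set the post-post correlation to 0.6, so that V = (1 + 1.2)/3 = 0.733 and unadjusted post-closure power is 71.5%. The adjusted variance is 0.733 − q²:
- q = 0.1: V = 0.723, power 72.0%, gain just under 1 point.
- q = 0.2: V = 0.693, power 73.8%, gain about 2.
- q = 0.3: V = 0.643, power 76.9%, gain about 5.

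**Relaxing equal variances.** Let the baseline SD be s times the post-closure SD. The four-visit variance is then (s² + 9×0.733 + 6qs)/16. With s = 0.25 and q = 0.2 this is (0.0625 + 6.6 + 0.3)/16 = 0.435, and power is 69.1% against 71.5% for post-closure visits alone. The power cost of including baseline nearly disappears, although the estimate is still 0.75 of the true mean difference.

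**The case against.** The strongest reply is that the plan never commits to the harmful analysis. A reader might infer that the trial will report effects shrunk by a quarter. That needs two choices the documents do not make: all four visits as outcome levels, and the arm main effect as the reported result. Section IV (ii) 2 puts the endpoint at 1 month, the general principles in Section X (ii) 1 offer a t-test or rank-sum test, and the ANOVA sentence allows a one-way analysis. A visit-by-visit or post-closure reading is therefore open, and it has no dilution. This objection stands: the shrinkage is conditional.

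A reader might also infer a large loss of power. The larger gains in the table need the pre-surgery score to predict post-closure scores well. The baseline is taken before resection, whereas the outcomes follow resection, diversion and closure, so the pre-post correlation could be well below the correlation among post-closure visits. The gain is then a few points. This also stands.

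Finally, a reader might infer that chance baseline imbalance under simple randomisation biases the comparison. It does not. An unadjusted post-closure comparison of randomised arms is valid, and its standard error already includes that variation. Imbalance is part of the precision argument and not a second harm.

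None of this gives a reason to leave the collected baseline unused. In the range examined, adjustment costs a negligible amount at zero correlation and helps otherwise.

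**Conclusion.** The point holds as a missed efficiency and an unspecified model; it does not show that the planned analysis is invalid. No baseline adjustment is stated for the three scores, although a suitable pre-treatment score is scheduled for every patient.

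The factor of 0.75 is exact with complete data, but applies only to the four-visit arm main effect. Against the valid alternative of unadjusted post-closure scores, the gain in power runs from nil to about 16 points for a common correlation of 0 to 0.5. It is about 1 to 5 points where the pre-surgery score is only weakly related to later scores. These figures rest on assumed values for the effect, variances and correlations, and the documents supply none of them. Only secondary endpoints are involved; the primary chi-square test of major LARS is unaffected.

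**What to change.** In Section X (ii) 2, state that for Wexner, MSKCC and QLQ-C30 the outcomes are the 1-, 3- and 6-month post-closure scores. The repeated-measures model should contain arm, visit, arm-by-visit and the pre-radical-surgery score as covariate. The result to report is the baseline-adjusted arm difference, including the 1-month contrast that Section IV names. This also settles which visits enter and which comparison is reported.

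This is a free improvement. It needs no new data or visits, because the pre-surgery questionnaires are already scheduled. It costs about one degree of freedom and a simple prespecified rule for missing baseline scores.
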